1.0 Background and Rationale

The acute leukemias in adults are characterized by resistance and poor outcomes. Acute myeloid leukemia (AML) and acute lymphoid leukemia (ALL) are aggressive malignancies that lead to the accumulation of immature myeloid or lymphoid precursors, resulting in progressive marrow failure and death ¹. They affect approximately 19,000 people per year in the United States; despite decades of research, the overall 5-year survival remains a disappointing 30-40% ²⁻⁴. The current treatment is intensive induction chemotherapy followed by consolidation using chemotherapy or a stem cell transplant ^{2,5}.

Selecting patients for intensive therapy is a major challenge in the acute leukemias.

There are multiple prognostic factors in the acute leukemias that are used to try and select the best candidates for intensive induction therapy. The most powerful single prognostic factor in the acute leukemias is cytogenetics. Using standard karyotyping techniques patients can be divided into 3 prognostic categories; good, intermediate and poor. They are characterized by 5 year overall survival rates of 55%, 24% and 5% respectively ⁶. Age is also a powerful prognostic factor in the acute leukemias. For patients over 60 with acute leukemia, the prognosis is grave (five-year survival of less than 10%)⁷⁻⁹. These patients have many co-morbidities and increased resistant disease ^{2,5}. Both acute leukemias in adulthood disproportionately affect the elderly (median age of onset of 72 and >60 for AML and ALL, respectively)^{4,10}. The presence of poorrisk cytogenetic factors is increased in elderly patients as well as expression of multi-drug efflux pumps ¹¹⁻¹². Performance status is another important prognostic factor and the ability to tolerate induction therapy decreases as performance status worsens regardless of age ⁸. For older patients with poor performance status it is currently acceptable clinical practice to offer only supportive care. In AML this has led some authors to conclude that standard induction chemotherapy should not be offered to elderly patients¹³. In contrast other groups have found a positive clinical impact of standard therapy in older AML patients with increased survival and less time in hospital than those offered only supportive care¹⁴. In order to better help clinicians decide what patients should be offered intensive therapy a number of prognostic scoring systems have been developed¹⁵. The majority of these systems rely heavily on the cytogenetics of the leukemia and this information is generally not available at the time of diagnosis. An additional prognostic factor that could be easily obtained at the time of diagnosis would a major step forward. In addition to deciding on what initial therapy to give an AML patient there is another major clinical decision point. A nadir marrow is obtained on day 14 following standard induction therapy and if there is significant residual disease a second course of induction is usually attempted. In many cases patients have experienced significant complications by day 14 making additional chemotherapy difficult to safely administer. There are very few studies on what prognostic factors are important when considering a second course of induction therapy. This is further complicated by the lack of rigorously performed studies to establish the predictive power of a positive nadir marrow. An additional prognostic factor that could be easily obtained on day 14 would be of significant help to clinicians.

Bioimpedance phase angle is prognostic in multiple disease states. Phase angle is measured by bioimpedance and reflects cell membrane integrity, nutritional status and muscle mass¹⁶. It has been found to be prognostic in a number of conditions such as end stage renal disease, HIV and COPD¹⁷⁻¹⁹. Additionally, it is prognostic in multiple tumor types including pancreatic, colorectal, breast and head and neck. In a recent report it was found to be strongly prognostic for patients with hematologic malignancies undergoing allogeneic stem cell transplants²⁰. Standardized phase angle measurements are made non-invasively, can be done quickly and reproducibly and with no patient discomfort. Measurements are taken by placing 2

electrodes on the hand and 2 on the foot from the same side of the patient. A small voltage is applied between the electrodes and the timing of induced the current is measured. The current is approximately 1000 times lower than the sensitivity of sensory neurons and thus cannot be felt by the patient and has no known biological effect. This study seeks to establish the feasibility and prognostic power of standardized phase angle in acute leukemia patients undergoing intensive induction chemotherapy.

2.0 Objectives

2.1 To determine the feasibility of obtaining standardized phase angle measurements on patients hospitalized for treatment of newly diagnosed acute leukemia.

2.2 To evaluate the association between standardized phase angle measured at the start of therapy and treatment-related outcomes including: Primary outcome: Treatment related mortality (defined as 60-day mortality) Secondary outcomes: Evaluate the association of the day 14 standardized phase angle and treatment related outcomes, 30-day mortality, length of hospitalization, transfer to intensive care unit during induction, treatment response (14 day bone marrow response, complete remission), receipt of post-remission therapy, overall survival.

2.3 An exploratory analysis investigating associations with the primary and secondary outcomes using different ways to categorize the baseline standardized phase angle measurement (obtained on the first day of treatment) and, for AML patients, the standardized phase angle measure obtained just prior to the nadir marrow.

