5.0 Data Management

All data will be de-identified and stored in a password protected REDCap database in accordance with HIPAA. Research Electronic Data Capture (REDCap) software is a secure, web-based application designed to support survey creation, survey administration and data capture for research studies. Records to be kept on each subject will include only the data specified in Appendices B, C, D, E and F. Only study personnel will have access to the data.

6.0 Registration

Eligible patients must be registered with the CCCWFU Registrar. Following registration, patients should have a baseline phase angle measurement taken. If a patient does not agree to have the measurement following registration, the patient's registration on the study may be canceled. The Registrar should be notified of cancellations as soon as possible.

To register a patient, the following documents should be completed by the research nurse or data manager and faxed [contact]) to the Registrar:

- Signed patient consent form/HIPAA authorization form
- On-Study/Registration Form (Appendix A)

The research nurse or data manager will then call [contact]) the Registrar between the hours of 0800-1600 EST Monday-Friday to verify eligibility. To complete the registration process, the Registrar will:

- assign a patient study number
- register the patient on the study

7.0 Statistical Considerations

Description of measures

Standardized phase angle

Standardized phase angle will be calculated as in 20 (standardized phase angle = (measured phase angle–phase angle ref)/SD ref). Reference values and standard deviation come from measurements of phase angle in over 200,000 healthy German adults²¹.

Mortality

30 day mortality rate is defined as the percent of patients no longer alive at 30 days after registration. In the rare case that a patient is lost to follow up before 30 days, the patient will be treated as missing.

60 day mortality rate is defined as the percent of patients no longer alive at 60 days after registration. Patients that are discharged to hospice care before 60 days without a known date of death will be counted towards 60 day mortality. In the rare case that a patient is lost to follow up before 60 days, the patient will be treated as missing.

Treatment response

14 day bone marrow response is defined as hypoplastic marrow with less than 20% cellularity and 5% blasts.

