Complete remission is defined as less than 5% marrow blasts, absolute neutrophil count >1000, platelet count >100,000 and freedom from red cell transfusions.

Feasibility Analysis

If the study fails to accrue 20 patients during the first year of accrual it will be deemed unlikely to meet its ultimate accrual goal and the study will be terminated.

Primary analysis

This study's primary endpoint is the association between standardized phase angle and 60 day mortality. Standardized phase angle will be treated as a continuous measure for the primary analysis. Since we will be using a standardized measure of phase angle, for power calculations we will assume a standard deviation of one and investigate the effects of a one unit change. A sample size of 102 patients would give us 80% power to detect an odds ratio of 2.1, using a logistic regression model with a 0.05 significance level and a 60 day mortality rate of 20%. With an expected accrual rate of 50 patients per year, the study should complete accrual in approximately two years and complete follow-up (two year follow-up) four years after the first patient is enrolled. Descriptive statistics will be used for baseline characteristics. Important baseline characteristics, such as age, will be added to the regression model as covariates for additional analysis.

Secondary analysis

We will use logistic regression to analyze the association between standardized phase angle and the secondary outcomes of 30 day mortality, transfer to the intensive care unit, 14 day marrow response, complete remission and receipt of post-remission therapy. The association with overall survival will be evaluated using a Cox proportional hazards model. We will use a linear model to look at the association with length of hospital stay. It is likely that the length of hospital stay will not be normally distributed and will need a transformation to satisfy the normality assumption of the linear model. Feasibility will be analyzed qualitatively.

Exploratory analysis

We will explore other versions of the standardized phase angle measure and how they relate to the primary and secondary outcomes. We will evaluate using categorical cut points of the baseline measure and the standardized phase angle measure captured just prior to the nadir marrow (for AML patients).

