Appendix E – Bone Marrow Biopsy and Treatment Data Collection Forms

BONE MARROW BIOPSY:
DATE//
Diagnosis: AML or ALL Blast %:
CYTOGENETICS:(free text)
RISK GROUP: FAVORABLE INTERMEDIATE UNFAVORABLE
APL: YESNO Hypoplastic marrow cellularity %:
TREATMENT:
HOSPITALIZED FOR INDUCTION CHEMOTHERAPY: Y N
DATE OF ADMISSION:
DATE OF DISCHARGE:
DATE INDUCTION CHEMOTHERAPY INITIATED:
TYPE OF CHEMOTHERAPY ADMINISTERED (check one):
 AraC+anthracycline+etoposide (7+3+3) AraC+ anthracycline (7+3) As per CALGB 10102 other(document regimen)
NUMBER OF CYCLES OF CHEMOTHERAPY:(range 0-5)
RESIDUAL DISEASE ON 14-DAY BONE MARROW BIOPSY: Y N N/A
REQUIRED ICU DURING HOSPITAL STAY: Y N
DEATH WITHIN 30 DAYS OF INITIAL TREATMENT: Y N
DEATH WITHIN 60 DAYS OF INITIAL TREATMENT: Y N
DISPOSITION: HOME SNFALF HOSPICE DECEASED
Need for total parenteral nutrition or feeding tube placement during induction hospitalization:

Y____ N____

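### ICU stays that precede the day-14 phase angle count as its outcome, because the plan sets no at-risk rule and Appendix E records ICU use without a date

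*Combined protocol and SAP*

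**What the plan says.** Objective 2.2 gives the secondary outcomes as one list: "association of the day 14 standardized phase angle and treatment related outcomes, 30-day mortality, length of hospitalization, transfer to intensive care unit during induction", followed by marrow response, remission, post-remission therapy and survival. Objective 2.3 and the exploratory analysis in Section 7 relate the phase angle taken before the nadir marrow, in AML patients, to the primary and secondary outcomes.

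The secondary analysis in Section 7 uses logistic regression for the "association between standardized phase angle and the secondary outcomes of 30 day mortality, transfer to the intensive care unit" and other binary outcomes. It does not say which of the two measurements is meant, and it does not define ICU transfer.

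The only ICU item on any form is in Appendix E: "REQUIRED ICU DURING HOSPITAL STAY: Y N". The same form has "DATE OF ADMISSION", the discharge date and "DATE INDUCTION CHEMOTHERAPY INITIATED", but no ICU date. Appendix D dates each phase angle measurement. Section 5.0 states: "Records to be kept on each subject will include only the data specified in Appendices B, C, D, E and F".

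**The concern.** A predictor measured around day 14 should be related to events that follow it. Here the outcome window opens when induction starts, so a patient who was in ICU on, say, day 6 enters the day-14 analysis as an event.

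The protocol itself makes early events likely. Section 1.0 says: "In many cases patients have experienced significant complications by day 14". Section 4 of the background discussion within 1.0 also describes phase angle as reflecting cell membrane integrity, nutrition and muscle mass, which critical illness could plausibly lower. A low day-14 value could then be a consequence of an ICU stay and yet be reported as a predictor of one.

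This bears on the stated purpose of the second measurement: "An additional prognostic factor that could be easily obtained on day 14 would be of significant help to clinicians". A clinician deciding on day 14 needs to know about risk from that day onward.

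**Working it through.** **Plan's own figure.** The plan gives no figure for ICU transfer. Its one sample size, 102 for the primary analysis (odds ratio 2.1 per SD, 20% mortality, 0.05 level, 80% power), is reproduced by simulation: power is 80.6% with a likelihood-ratio test and 78.9% with a Wald test. The present point does not depend on it.

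**Inputs.** From the documents: phase angle SD of 1, logistic regression, 0.05 level. Assumed, because the documents give no AML count, ICU rate or size of drop:
- 70 AML patients with a day-14 value
- later ICU transfer in 15%, unrelated to phase angle
- early ICU stay in a share *e* of 2–15%
- a drop *d* of 0.25–1.0 SD in phase angle after an early stay

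**Closed-form approximation.** Share with any ICU stay: p = 1 − (1 − e)(0.85). Share of those whose stay includes an early one: s = e/p. Mean phase angle is lower by s·d in the ICU group. Pooled variance: v = 1 + p·s(1 − s)·d². Log odds ratio per unit lower ≈ s·d/v.
- e = 2%, d = 0.5: p = 0.167, s = 0.120, s·d = 0.060, v = 1.004, odds ratio 1.06.
- e = 10%, d = 0.5: p = 0.235, s = 0.426, s·d = 0.213, v = 1.014, odds ratio 1.23.
- e = 15%, d = 1.0: p = 0.2775, s = 0.541, s·d = 0.541, v = 1.069, odds ratio 1.66.

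**Simulation.** 5,000 runs per cell, Wald test, any ICU stay as the outcome. Cells show the odds ratio per unit lower and the rejection rate; the true odds ratio is 1.

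| Early ICU | 0.25 SD drop | 0.5 SD drop | 1.0 SD drop |
|---|---|---|---|
| 2% | 1.04, 4.6% | 1.07, 5.0% | 1.13, 5.8% |
| 5% | 1.06, 5.3% | 1.14, 6.7% | 1.29, 12.7% |
| 10% | 1.12, 6.1% | 1.24, 10.8% | 1.50, 28.3% |
| 15% | 1.15, 7.2% | 1.31, 16.3% | 1.68, 46.0% |

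With no drop, the odds ratio is 1.00 and rejection is 4.4–4.9%. The number of AML patients matters most in the worst cell (15%, 1.0 SD): rejection is 32.5% with 50 patients and 57.0% with 90.

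**Alternatives.**
- Early-ICU patients left out, only later transfers counted (landmark analysis): odds ratio 0.99–1.01, rejection 3.7–4.4%. If early-ICU patients have a 40% later risk, it is 0.99–1.01 and 3.5–4.8%.
- Later transfers counted in everyone, 40% later risk after an early stay: worst cell 1.21, 10.0%.
- First-transfer date used, but early-ICU patients kept as non-events: 0.85 at 15% and 1.0 SD. The bias is now in the other direction.

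**Price in precision.** Expected events as planned: 70 × (1 − 0.98 × 0.85) = 11.7 to 70 × (1 − 0.85 × 0.85) = 19.4. Landmark: 68.6 × 0.15 = 10.3 to 59.5 × 0.15 = 8.9. Standard error of the log odds ratio: 0.356 against 0.336 (2%, 0.5 SD; ratio 1.06) and 0.384 against 0.282 (15%, 1.0 SD; ratio 1.36).

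**The case against.** **Objective 2.2 is ambiguous.** Its stem concerns phase angle at the start of therapy, so ICU transfer may be listed there as an outcome of the baseline value. That reading is fair. It makes the explicit day-14 link exploratory, but does not remove it, because Objective 2.3 and Section 7 make the link separately.

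**The dates are not lost.** A reader might infer from Section 5.0 that the order of events can never be recovered. The documents do not support that. The list in Section 5.0 omits Appendix G, the survival form, so it is visibly incomplete, and hospital records may hold ICU dates. Patients with no ICU stay need no ordering, and a discharge before the second measurement would place a stay early. What stands is that the planned data generally cannot order the two events for other patients with an ICU stay.

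**The landmark analysis drops patients with early complications**, a group the background highlights. This is a real cost, and a reason to report all later transfers as a sensitivity analysis.

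**Stronger readings to avoid.** A reader might infer that the baseline ICU analysis is equally affected, since Appendix E covers the whole stay. Nothing in the documents suggests that ICU stays before the baseline measurement are common; patients must be able to consent, and Appendix A requires registration before treatment. A reader might also infer that the differing descriptions of measurement timing (Section 4.0 against Objective 2.3, Section 9.0 and Appendix D) leave the meaning of earlier and later undefined. Appendix D records the actual date, so that wording is a separate matter of reconciling passages.

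**Conclusion.** The point holds for the day-14 ICU analysis in AML patients. As planned, that analysis counts ICU stays that came before the predictor, and the planned forms generally cannot separate them. Whether this distorts the result depends on two unknowns: how many patients have an early ICU stay and how far it lowers phase angle. A 0.25 SD drop gives false-positive rates of 5–7%, which is negligible to minor. The 46% figure needs a full SD drop and early stays in about half of ICU patients (0.15/0.2775 = 54%). All these inputs are assumptions.

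Only a secondary or exploratory analysis is affected; the primary 60-day mortality analysis and its sample size are not. The change is worth making because it is cheap, and because without dates the study could not show which end of the range applies.

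**What to change.** 1. Add the date of first ICU transfer to Appendix E, taken from the hospital record. This one field is enough for the main analysis.
2. State in Section 7 that the day-14 ICU analysis includes only AML patients with no ICU transfer before the Appendix D date of the second measurement, and counts only later transfers. Say explicitly that early-ICU patients are left out and not kept as non-events, and how a transfer on the measurement date itself is classed.
3. Optionally, record the first transfer after the measurement as well, so that later transfers in all patients can be reported as a sensitivity analysis.
4. Use the same date to check whether any ICU stay came before the baseline measurement.

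The cost is one or two date fields and a few sentences, plus the loss of events and precision shown in the working.

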3.0 Patient Selection Criteria

3.1 Eligible

- 3.11 Hospitalized for newly diagnosed acute leukemia
- 3.12 Receiving induction treatment while hospitalized
- 3.13 Willing and able to provide written informed consent

3.2 Ineligible

- 3.21 Presence of a pacemaker or defibrillator.
- 3.22 Patients pregnant at the time of enrollment.
- 3.23 Any condition or abnormality which may, in the opinion of the investigator, compromise the safety of patients.
- 3.24 Unable/unwilling to follow protocol requirements

4.0 Study Design

Eligible patients with newly diagnosed acute leukemia will have phase angle measurements recorded within the first 3 days of treatment. AML patients will have a second phase angle measurement taken within 2 days of the nadir marrow. Whenever possible, measurements will be taken prior to any invasive procedures (bone marrow biopsy, leukophoresis, PICC line placement, etc.). In addition data on pertinent covariates including age, demographic data, tumor biology, white blood cell count, LDH, need of total parental nutrition or placement of a feeding tube and comorbid conditions

will be collected. There will be no intervention done as a result of the phase angle measurement. Patients will be followed at routine visits per standard of care for two years or until death.

5.0 Data Management

All data will be de-identified and stored in a password protected REDCap database in accordance with HIPAA. Research Electronic Data Capture (REDCap) software is a secure, web-based application designed to support survey creation, survey administration and data capture for research studies. Records to be kept on each subject will include only the data specified in Appendices B, C, D, E and F. Only study personnel will have access to the data.

6.0 Registration

Eligible patients must be registered with the CCCWFU Registrar. Following registration, patients should have a baseline phase angle measurement taken. If a patient does not agree to have the measurement following registration, the patient's registration on the study may be canceled. The Registrar should be notified of cancellations as soon as possible.

To register a patient, the following documents should be completed by the research nurse or data manager and faxed [contact]) to the Registrar:

- Signed patient consent form/HIPAA authorization form
- On-Study/Registration Form (Appendix A)

The research nurse or data manager will then call [contact]) the Registrar between the hours of 0800-1600 EST Monday-Friday to verify eligibility. To complete the registration process, the Registrar will:

- assign a patient study number
- register the patient on the study

7.0 Statistical Considerations

Description of measures

Standardized phase angle

Standardized phase angle will be calculated as in 20 (standardized phase angle = (measured phase angle–phase angle ref)/SD ref). Reference values and standard deviation come from measurements of phase angle in over 200,000 healthy German adults²¹.

Mortality

30 day mortality rate is defined as the percent of patients no longer alive at 30 days after registration. In the rare case that a patient is lost to follow up before 30 days, the patient will be treated as missing.

60 day mortality rate is defined as the percent of patients no longer alive at 60 days after registration. Patients that are discharged to hospice care before 60 days without a known date of death will be counted towards 60 day mortality. In the rare case that a patient is lost to follow up before 60 days, the patient will be treated as missing.

Treatment response

14 day bone marrow response is defined as hypoplastic marrow with less than 20% cellularity and 5% blasts.

Complete remission is defined as less than 5% marrow blasts, absolute neutrophil count >1000, platelet count >100,000 and freedom from red cell transfusions.

Feasibility Analysis

If the study fails to accrue 20 patients during the first year of accrual it will be deemed unlikely to meet its ultimate accrual goal and the study will be terminated.

Primary analysis

This study's primary endpoint is the association between standardized phase angle and 60 day mortality. Standardized phase angle will be treated as a continuous measure for the primary analysis. Since we will be using a standardized measure of phase angle, for power calculations we will assume a standard deviation of one and investigate the effects of a one unit change. A sample size of 102 patients would give us 80% power to detect an odds ratio of 2.1, using a logistic regression model with a 0.05 significance level and a 60 day mortality rate of 20%. With an expected accrual rate of 50 patients per year, the study should complete accrual in approximately two years and complete follow-up (two year follow-up) four years after the first patient is enrolled. Descriptive statistics will be used for baseline characteristics. Important baseline characteristics, such as age, will be added to the regression model as covariates for additional analysis.

Secondary analysis

We will use logistic regression to analyze the association between standardized phase angle and the secondary outcomes of 30 day mortality, transfer to the intensive care unit, 14 day marrow response, complete remission and receipt of post-remission therapy. The association with overall survival will be evaluated using a Cox proportional hazards model. We will use a linear model to look at the association with length of hospital stay. It is likely that the length of hospital stay will not be normally distributed and will need a transformation to satisfy the normality assumption of the linear model. Feasibility will be analyzed qualitatively.

Exploratory analysis

We will explore other versions of the standardized phase angle measure and how they relate to the primary and secondary outcomes. We will evaluate using categorical cut points of the baseline measure and the standardized phase angle measure captured just prior to the nadir marrow (for AML patients).

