Appendix G – Survival Data

Visit Date: ____ / ____ / ____

Visit Interval:

_____ 3 Mos Post _____ 6 Mos Post _____ 9 Mos Post _____ 12 Mos Post

_____ 15 Mos Post _____ 18 Mos Post _____ 21 Mos Post _____ 24 Mos Post

_____ Other Mos Post _____ Number of Months Post Discharge

DATE OF LAST CONTACT: ____ / ____ / ____

DECEASED: Y____N___

DATE OF DEATH: ____ / ____ / ____

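### An undated hospice discharge counts as a death for 60-day mortality, but 30-day mortality and overall survival have no matching rule

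*Combined protocol and SAP*

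**What the plan says.** Section 7.0, under Mortality, defines the two early endpoints in adjacent paragraphs. For the first: "30 day mortality rate is defined as the percent of patients no longer alive at 30 days after registration". Its only rule for incomplete follow-up is "In the rare case that a patient is lost to follow up before 30 days, the patient will be treated as missing".

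The 60-day paragraph has the same rule for loss to follow-up, "In the rare case that a patient is lost to follow up before 60 days, the patient will be treated as missing", and adds one for hospice: "Patients that are discharged to hospice care before 60 days without a known date of death will be counted towards 60 day mortality".

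Overall survival gets one sentence, in Section 7.0 under Secondary analysis: "The association with overall survival will be evaluated using a Cox proportional hazards model". No event date, censoring date or hospice rule is given for it.

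Section 4.0 describes follow-up: "Patients will be followed at routine visits per standard of care for two years or until death". Appendix E records hospice as a discharge disposition, the discharge date, and death within 30 and 60 days as yes/no. Appendix G records date of last contact, deceased status and date of death every three months from month 3, with an option for other times.

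**The concern.** By writing the hospice rule, the plan accepts that an undated hospice discharge is strong evidence of death by day 60. The other two endpoints make no use of that evidence. At 30 days a patient with unknown status has nowhere to go except the lost-to-follow-up rule, which removes the patient. In a Cox model with no stated rule, the usual practice is to censor at last contact, which may be the day of hospice discharge. That treats the patient as having the same outlook as those still followed at that time.

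The patients who leave the risk set in this way are close to death. If frailer patients, with lower phase angle, go to hospice more often, both associations are pulled toward no effect. Overall survival could also disagree with the trial's own 60-day mortality. Follow-up at routine visits makes an undated death more likely, because a hospice patient may not attend them.

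**Working it through.** **Step 1. The plan's own figure.** Inputs from Section 7.0: odds ratio 2.1 per unit, standard deviation 1, 60-day mortality 20%, significance level 0.05, power 80%. A likelihood-ratio test for logistic regression on one standard normal covariate (noncentral chi-square, 1 degree of freedom, two-sided, overall event rate 20%) needs n = 101.1, which rounds up to 102; power at 102 is 80.3%. The planned N reproduces. It rests on the 60-day endpoint, which has its hospice rule, so this point does not touch it. Expected 60-day deaths: 0.20 × 102 = 20.4, about 20.

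**Step 2. The rules applied patient by patient.**

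| Patient discharged to hospice before day 60 | 60-day mortality | 30-day mortality | Overall survival |
|---|---|---|---|
| No death date; left before day 30; day-30 status unknown | death | missing | no rule; the default censors at last contact |
| No death date; left before day 30; known alive at day 30 | death | alive | no rule; the default censors at last contact |
| No death date; left on days 30 to 60 | death | alive | no rule; the default censors at last contact |
| Death date known | by date | by date | event on that date |

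Only the first row loses a patient from 30-day mortality. The first three rows leave overall survival undefined.

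**Step 3. The 30-day rate.** The documents give neither a 30-day rate nor a number of such patients. Assume D = 10 known deaths by day 30 and h patients in the first row.

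- Treated as missing: D/(102 − h). Counted as deaths: (D + h)/102. Counted as survivors: D/102 = 9.8%.
- h = 1: 10/101 = 9.9% against 11/102 = 10.8%.
- h = 2: 10/100 = 10.0% against 12/102 = 11.8%.
- h = 4: 10/98 = 10.2% against 14/102 = 13.7%.
- h = 6: 10/96 = 10.4% against 16/102 = 15.7%.

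The gap between missing and death runs from about 1 to about 5 points. At h = 6 it is similar with D = 8 (8.3% against 13.7%) and D = 15 (15.6% against 20.6%).

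**Step 4. The associations, by simulation.** Assumptions:

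- Weibull survival, 20% dead by day 60 (the plan's figure) and 55% by two years (assumed).
- Hazard ratio 1.9 per unit lower phase angle (assumed; about the plan's odds ratio of 2.1 at day 60).
- Hospice discharge 3 to 21 days before death (assumed).
- A stated share of 60-day deaths are undated hospice discharges. Their odds double per unit lower phase angle, except in the last row.
- Such patients are missing at 30 days if discharged before day 30, and are censored at discharge in the Cox model.

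| Share of 60-day deaths | 30-day odds ratio, full data → as planned | Hazard ratio, full data → default censoring |
|---|---|---|
| 5% (about 1 of 20) | 2.05 → 1.99 | 1.91 → 1.88 |
| 10% (about 2 of 20) | 2.12 → 1.98 | 1.93 → 1.89 |
| 25% (about 5 of 20) | 2.03 → 1.74 | 1.91 → 1.82 |
| 50% (about 10 of 20) | 2.05 → 1.50 | 1.90 → 1.76 |
| 25% or 50%, hospice unrelated to phase angle | hardly moves | hardly moves |

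Full-data values differ between rows by simulation error. Repeat runs at 25% gave 1.76 to 1.79 for the odds ratio and 1.80 to 1.81 for the hazard ratio. At 25%, counting the dropped patients as 30-day deaths gives an odds ratio of 2.09, and setting death at day 60 gives a hazard ratio of 1.87.

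**Step 5. Against sampling error.** With 0.55 × 102 = 56 deaths, the standard error of the log hazard ratio is about 1/√56 = 0.13. The shift at 25% is ln(1.91/1.82) = 0.048, under half of that.

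**The case against.** The strongest case against is that this is a gap in wording with little consequence. The primary endpoint has an explicit hospice rule. The number of affected patients may be one or two, and at that level the estimates barely change. Presumed death by day 60 does not imply death by day 30, so leaving hospice discharge unimputed at 30 days could be deliberate. All of this stands, and it sets the size of the point. What it does not answer is the removal of patients at 30 days. Excluding someone whom the plan presumes dead a month later is not the same as declining to impute a death.

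Four stronger readings are tempting, and the documents do not support them.

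- A reader might infer that the plan censors hospice patients as alive in overall survival. It does not say so. It names a Cox model and gives no censoring rule; censoring at last contact is only the usual default.
- A reader might infer that every hospice patient is dropped from 30-day mortality. Only an undated discharge before day 30 with unknown day-30 status is affected.
- A reader might infer from the yes/no death items in Appendix E that no dates are collected. Appendix G has fields for date of death and for "DATE OF LAST CONTACT", so a date learned later can be entered.
- A reader might conclude that every patient scored under the 60-day rule should be entered as dead by day 60 in the Cox model. Read literally, the rule also covers a patient seen alive at three months with no death date, and that would create a false event.

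The same simulation would also show Kaplan-Meier survival at day 60 of about 85% instead of 80% at the 25% share. The plan specifies no Kaplan-Meier estimate, so the conclusion does not rest on that figure.

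**Conclusion.** The point holds as a minor one, confined to two secondary endpoints. The hospice rule exists for 60-day mortality alone. One consequence follows from the stated rules: an undated hospice discharge before day 30 with unknown day-30 status is missing from 30-day mortality. The other follows from the absence of a rule: overall survival would, by default, treat the same discharge as uninformative, against the judgement made for the 60-day endpoint.

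The size depends on two things the documents do not give: how many such patients there will be, and whether hospice choice tracks phase angle. A material shift needs both a share of around a quarter of 60-day deaths and a clear link to phase angle. The 30-day odds ratio then falls to about 1.75 and the hazard ratio to about 1.8. Patients with a known death date are unaffected on all endpoints, and those known to be alive at day 30 are unaffected at 30 days. The primary analysis and the sample size stand.

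**What to change.** 1. **Section 7.0, 30-day mortality.** Do not drop patients discharged to hospice before day 30 with unknown day-30 status. Report the association twice, with them counted as deaths and as survivors to day 30.
2. **Section 7.0, overall survival.** State the censoring rule. Add a sensitivity analysis in which a patient counted as a 60-day death under the hospice rule, and with no documented contact alive after day 60, has an event at day 60 instead of being censored at last contact. As an alternative, place the event at hospice discharge.
3. **Section 4.0 with Appendices E and G.** For patients whose Appendix E disposition is hospice, check vital status and date of death by chart or telephone at day 60 and at the Appendix G intervals. Use the actual date wherever one is found. This does the most good, because a known date removes the problem on all three endpoints.

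The cost is a few sentences in Section 7.0, a small number of extra model runs and a few chart or telephone checks. The downside is approximate death times for a few patients, and only in the sensitivity analysis. Setting death at day 60 also recovers only part of the attenuation (1.87 against 1.91 in the 25% case).
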